6. OBJECTIVES AND OUTCOME MEASURES

		Outcome Measures	Timepoint(s)
Primary Objective To evaluate the diagnostic non-contrast enhanced (no ultrasound scans (USS) as s for the diagnosis of hepato (HCC).	ceMRI) and surveillance tools	True positive tests for HCC per round of surveillance False positive tests for HCC per round of surveillance Positive predictive value for HCC per round of surveillance True negative tests for HCC over the 30 months of surveillance False negative tests for HCC over the 30 months of surveillance Sensitivity and specificity of nceMRI and USS for HCC over 30 months of surveillance	Per round of surveillance analysis will be done for each visit: Baseline, visits 2, 3, 4, 5 and 6 For the 30 months of surveillance, analysis will be done for the entire 30 months of surveillance
Secondary objectives			
To determine the stage an diagnosis and the number lesions detected		Numbers of HCC detected by nceMRI and USS at a very early, early, intermediate or advanced stage as defined by the Barcelona Clinic Liver Cancer staging system.	At each 6 monthly surveillance round (Baseline, visits 2, 3, 4, 5 and 6

To determine the proportion of patients that receive treatment with curative intent	The number and size of HCC tumours per participant with HCC The number of new indeterminate lesions identified at each surveillance round Proportion of participants diagnosed with HCC who go on to receive treatment with curative intent	At any time point an HCC is diagnosed, the analysis will be conducted once all participants complete the			
To evaluate the impact of the modality used for HCC surveillance on quality of life (QoL) and anxiety and depression	Results of the EQ-5D-5L questionnaire and Hospital Anxiety and Depression Scale questionnaire	study. At each 6 monthly surveillance round (Baseline, visits 2, 3, 4, 5 and 6			
To evaluate the participants' attitude, experience, and acceptability of nceMRI and USS for HCC surveillance	Results of participant experience questionnaire	Baseline, visit 5			
To evaluate the feasibility of nceMRI and USS as surveillance tools for HCC	Number of missed appointments (cancelled or missed), number of participants lost to follow-up, Number of participants where HCC surveillance is no longer indicated	At the end of the study			

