7. STUDY DESIGN

This will be a single-arm, multi-centre, prospective cohort study evaluating the diagnostic accuracy of nceMRI and USS for diagnosis of HCC in people at high risk of HCC. People at high risk of HCC include those with liver cirrhosis and a high risk of HCC, or those with previous successfully treated HCC who are back in surveillance with USS. Participants will be recruited from UK hospital-based liver clinics over a period of 18 months and study procedures will take place in UK hospitals and academic centres. Participants will undergo 6 rounds of 6 monthly surveillance with nceMRI and USS over 30 months. Participants will be invited to complete questionnaires at each study visit. Relevant data will also be extracted from the participants' medical records. If at any surveillance round, a surveillance test raises a concern for the presence of HCC, participants will undergo full diagnostic contrast enhanced MRI (ceMRI) to determine whether HCC is present or not. In cases where indeterminate lesions for HCC are reported, these may require further tests including contrast CT, follow-up contrast enhanced MRI, or biopsy as directed by the clinical team. All participants will undergo diagnostic full contrast enhanced MRI at the end of their study participation. If an HCC is diagnosed at any point in the study, then participants will receive treatment according to standard clinical protocols as part of standard of care.

Long-term follow up of medical records from NHS England, the NHS Central Register for Scotland and other patient registries may be conducted for up to 10 years after the end of the active follow up phase. Data obtained from these registries will include but is not limited to liver disease, decompensation episodes, HCC diagnosis, liver transplantation and death. There will be no additional involvement from study sites or participants, as the long-term follow up only involves accessing centrally held medical data.

The overall study design and participant flow is summarised in Figure 1.

Figure 1: AMULET study design and patient flow

Abbreviations: HCC: hepatocellular cancer; USS: ultrasound scan; nceMRI: non-contrast enhanced MRI; AFP: alpha-fetoprotein; HADS: hospital anxiety and depression scale; +ve: positive; -ve: negative [#] see section 9.4 for the description of the procedure for HCC risk estimation

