9.8.1. Description of comparator(s)

The comparator will be the diagnosis of hepatocellular carcinoma based on the typical features on contrast enhanced MRI or CT or histological diagnosis (biopsy or resection) or a consensus diagnosis of HCC as determined by the local MDT will be accepted as a diagnosis of HCC.

On study contrast enhanced MRI scans

For cases where a contrast enhanced MR is done following a positive surveillance test (on study ceMRI), lesions classified as LI-RADS 1 or 2 will be regarded as negative for HCC and lesions classified as LI-RADS 5 will be regarded as positive for HCC. Lesions classified as LI-RADS 3 or 4 will be regarded as indeterminate and will be followed up according to the local clinical routine. If LI-RADS 3 or 4 are designated as HCC by the local MDT, or they are proven to be HCC on biopsy, or they progress to LI-RADS 5 within the 30 months of follow-up then they will be defined as HCC for the analysis relating to the whole 30 month period of surveillance. In cases where LI-RADS 3 or 4 lesions remain under follow-up at the end of the 30 months follow-up without a clear classification as HCC or benign, or where they have been histologically proven to be benign, then they will be classified as negative for HCC for the purposes of the analysis. The classification of lesions at on-study ceMRI scans is shown below in Figure 2. The follow-up of LI-RADS 3 and 4 lesions in this situation will finish at the timepoint that visit 6 was due or at an earlier time point if a definitive classification is reached before then.

Figure 2: Flowchart for the classification of lesions detected on contrast enhanced MRI performed during the study following a positive surveillance test. In cases where lesions are determined as negative within the 30-month surveillance period, participants will re-enter the AMULET surveillance schedule until they complete the study. Where a positive for HCC diagnosis is made, participants will end their participation, will undergo no further surveillance and will be managed according to the recommendations of the local MDT. Participants with LI-RADS 3 or 4 lesions who are undergoing interval contrast enhanced imaging as recommended by the local MDT will be suspended from participation in AMULET.

End of Study contrast enhanced MRI scan

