9.10. Subsequent Study Visits

At each subsequent visit, the patient's eligibility to the study will be checked and patients will undergo another formal safety assessment before undergoing MR examinations. Patients will have to attend their MRI having fasted for at least 4 hours.

Each follow up visit will ideally take place on a single day but may take place on two separate days, with the first imaging scan and data collection taking place up to 28 days prior to the second imaging scan (see also section 9.7).

Participants will attend follow-up every 180 days for five visits after baseline (total of six visits including baseline). At each subsequent visit, confirmation of continuous consent will be obtained from the participant and an eligibility check will be carried out to ensure that participants still fulfil the inclusion and exclusion criteria.

Study visits will last for 120 minutes and assessments/procedures are as follows:

- Collection of Demographics and Medical History (duration 10 minutes)
- Physical Examination (recording of height and weight) (duration 5 minutes)
- Completion of MRI safety check (5 minutes)
- Clinical care USS (20 Mins)
- nceMRI (20 minutes)
- Completion of EQ-5D-5L and HADS questionnaires at the beginning of each study visit (30 minutes)
- Acceptability of MRI and USS as surveillance test questionnaire (to be completed immediately after the relevant scan on visit 5 only, 30 minutes)

Visit 6, final study visit (120 minutes)

At visit 6, in addition to the other study procedures listed above, a contrast enhanced MRI will be performed on all participants.

Contrast enhanced MRI will also be performed at any visit if the surveillance USS or nceMRI show a suspicious nodule for HCC.

Timing between visits

The baseline visit (visit 1) will be designated as D0. If the study procedures take place on different days for the baseline visit then D0 will be the first day on which study procedures were carried out. Once the baseline visit is completed, dates will be assigned for subsequent visits (visit 2: D180, visit 3: D360; visit 4: D540 etc).

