9.11. Follow Up

Follow up visits/procedures after specific clinical outcomes (HCC diagnosis/liver transplant and death)

HCC Diagnosis

If a diagnosis of HCC is made during the study, no further in person follow up visits or nceMRI scans will take place. Follow up data will continue to be collected at 6 monthly intervals from hospital records.

Liver Transplant

If a participant receives a liver transplant during the study, no further in person follow up visits or nceMRI scans will take place. Follow up data will continue to be collected at 6 monthly intervals from hospital records.

Death

If a participant dies, the date and cause of death should be clearly documented using the 'Mortality' form within REDCap. In the event that a participant's death certificate is not available on hospital records, the local study team may be asked to contact the relevant GP to obtain date/cause of death data.

Long-Term Follow-up

The study teams will obtain data from NHS England, the NHS Central Register for Scotland and other patient registries on participants for up to 10 years after the last follow-up visit, phone call or email. This will be a passive follow-up with no participant involvement.

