11.2. Description of the Statistical Methods

Statistical analysis for Primary outcome measure

Measures of diagnostic performance will be determined per round of surveillance and over the 30 months of study participation.

Diagnostic performance per round of surveillance

At each round of surveillance, the following data will be calculated and compared between USS and nceMRI.

- 1. Number and proportions of positive surveillance USS and nceMRI see section 9 for definitions of positive tests
- Number and proportions of true positive (TP) and false positive (FP) USS and nceMRI. As each positive test will be followed by a full contrast enhanced MRI, TP and FP tests per round of surveillance will be calculated
- 3. Positive predictive value (PPV) of USS and nceMRI

Diagnostic performance for the overall study period of 30 months

For the purpose of this analysis, each USS and nceMRI scan for each participant completing the study will be assigned only one of the 4 possible diagnostic categories of: true positive (TP) or false positive (FP), true negative (TN) and false negative (FN). The sum of TP, FP, TN and FN in this analysis will therefore be equal to the total number of participants completing the study. TP and FP will be determined at each visit as described above. TN and FN will be determined at the end of the study when participants undergo the reference standard ceMRI as part of the study protocol. FN results will also include those cases that present with HCC during the study without a prior positive test (interval cancers) or cases where both USS and nceMRI are negative tests but a ceMRI scan is triggered by an AFP>20. Cases that are initially FP may subsequently change diagnostic category. For this analysis, the diagnostic category which is applicable at the end of the study will be used. For example, if a finding initially classed as an FP develops into an HCC that was correctly identified by the surveillance tests, then the diagnostic test will be counted as a TP for this analysis.

Sensitivity and specificity estimates will be calculated separately for nceMRI and USS and compared. Statistical significance of the observed differences in sensitivity/specificity will be evaluated using the McNemar's test of paired proportions, with a two-tailed P-value <0.05 used as the significance criteria.

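### The primary outcome is labelled as sensitivity over 30 months, but the scoring gives paired sensitivity at the round of first diagnosis, not what either test would achieve alone over 30 months

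*Protocol*

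**What the plan says.** Sections 3 and 6 of the protocol separate per-round outcomes (true positives, false positives, positive predictive value) from outcomes for the whole period, and put sensitivity in the second group: "Sensitivity and specificity of nceMRI and USS for HCC over 30 months of surveillance". Section 11.2 analyses it under the overall 30-month period.

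The rules that produce the number are these:

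- Section 7: "Participants will undergo 6 rounds of 6 monthly surveillance with nceMRI and USS over 30 months".
- Section 9.10: "Contrast enhanced MRI will also be performed at any visit if the surveillance USS or nceMRI show a suspicious nodule for HCC". One positive test is enough.
- Section 9.8.1: "Where a positive for HCC diagnosis is made, participants will end their participation, will undergo no further surveillance". Section 9.11 agrees: "If a diagnosis of HCC is made during the study, no further in person follow up visits or nceMRI scans will take place".
- Section 11.2: for each participant, each test "will be assigned only one of the 4 possible diagnostic categories", and "TP and FP will be determined at each visit as described above". The only later change of category described is for findings first classed as false positive.
- Section 11.8: a test not done at the visit where HCC is diagnosed is scored as a false negative.

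One secondary outcome in section 6 is "Numbers of HCC detected by nceMRI and USS at a very early, early, intermediate or advanced stage as defined by" the BCLC system, counted for each test.

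**The concern.** Suppose nceMRI alone finds a cancer at visit 2. Surveillance ends and USS is scored as having missed it. A participant under 30 months of USS alone would have had four more scans, at visits 3 to 6. If instead both tests are negative at visit 2 and one or both find the cancer at visit 3, the earlier miss leaves no trace in the score of the test that finds it. A miss by one test is final, while a miss by both is usually followed by another paired look.

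The result is neither single-scan sensitivity nor the sensitivity of a 30-month programme with one test. This matters because section 5.4 presents nceMRI as a possible replacement for USS. A reader choosing between programmes will take a 30-month sensitivity as what each would achieve alone, and this design does not observe that.

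The stage outcome is affected too. HCCs found by both tests in the same round enter both counts identically. HCCs that nceMRI finds first never show the stage at which USS would have found them.

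**Working it through.** **1. The plan's own figure.** Section 11.3 uses McNemar's test with 90% power and 5% type 1 error (two-sided in section 11.2). For nceMRI 80% and USS 50%, Table 2 gives 50 HCCs. A correlation (phi) of 0.1 between the tests, which the protocol does not state, reproduces all nine sensitivity cells. For this cell:

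- Covariance: 0.1 × √(0.8×0.2×0.5×0.5) = 0.02
- Both detect: 0.40 + 0.02 = 0.42; nceMRI only: 0.38; USS only: 0.08; both miss: q = 0.12
- Discordance 0.46, difference 0.30
- n = [1.96√0.46 + 1.282√(0.46 − 0.09)]² / 0.09 = 49.4, so 50

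**2. As scored against stand-alone, misses independent between rounds.** Assumptions: 80% and 50% are per-round sensitivities; onset is spread evenly, so a cancer has m = 1 to 6 rounds left with equal probability; there are no interval or AFP-triggered cancers.

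- As scored, a test with sensitivity s has s(1 − q^m)/(1 − q). For q = 0.12 the multiplier averages (1 + 1.12 + 1.1344 + 1.1361 + 1.1363 + 1.1364)/6 = 1.1105. This gives nceMRI 0.888 and USS 0.555, a gap of 33.3 points.
- Stand-alone is 1 − (1 − s)^m. Averaged over m, this gives nceMRI 0.958 and USS 0.836, a gap of 12.2 points.

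**3. Why the gaps differ.** As-scored gap minus stand-alone gap = (share of HCCs nceMRI finds first that USS would find later) − (share USS finds first that nceMRI would find later). Here (0.836 − 0.555) − (0.958 − 0.888) = 0.281 − 0.070 = 0.211.

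**4. Misses that tend to repeat.** The same set-up, with a shared latent (probit) component between rounds, equally strong for both tests:

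| Between-round latent correlation | As scored, nceMRI / USS | Gap | Stand-alone, nceMRI / USS | Gap | Excess |
|---|---|---|---|---|---|
| 0 | 88.8 / 55.5 | 33.3 | 95.8 / 83.6 | 12.2 | 21.1 |
| 0.5 | 87.1 / 54.0 | 33.1 | 93.1 / 73.5 | 19.7 | 13.4 |
| 0.8 | 84.9 / 52.6 | 32.3 | 89.1 / 64.6 | 24.5 | 7.8 |
| 0.95 | 82.7 / 51.4 | 31.3 | 84.9 / 57.3 | 27.6 | 3.7 |
| 1 (full repetition), or one round left | 80 / 50 | 30 | 80 / 50 | 30 | 0 |

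**5. Where the direction can fail.** If only USS misses repeated fully while nceMRI misses were independent, the first share in step 3 would be nil. The second would be 0.08 × the mean of 1 − 0.16^(m−1), with 0.16 = 1 − 0.42/0.50. That is 0.08 × 0.80 = 0.064, so the scored gap would be about 6 points too small. The stated direction needs misses of roughly similar persistence in the two tests.

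**6. What the trial's own data could bound (independent case).** HCCs found by nceMRI alone before visit 6 have the multiplier (0 + 1 + 1.12 + 1.1344 + 1.1361 + 1.1363)/6 = 0.921, and 0.38 × 0.921 = 0.350, or about 17 or 18 of 50. USS alone over 30 months would then lie between 55.5% and 55.5 + 35.0 = 90.5%. For nceMRI, 0.08 × 0.921 = 0.074 gives 88.8% to 96.2%. These two ranges hold only for independent misses.

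**The case against.** The strongest reply is that nothing here is an error. Section 7 describes a single-arm paired accuracy study, and section 11.2 defines the quantity: one category per test per participant, with most negatives verifiable only at the end-of-study scan. On that reading the 30-month label only separates the pooled analysis from the per-round one, and the protocol never claims to compare stand-alone programmes.

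Part of this stands. Ending both tests at a confirmed HCC is inherent in the paired design and is not at issue here. McNemar's test is valid for the quantity scored. What does not stand is that the label is harmless: the protocol separates per-round from 30-month performance, places sensitivity only under the latter, and motivates the study by replacing one surveillance test with the other. Nowhere does it say that its sensitivity is conditional on the round of first diagnosis.

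The reply is also right on several limits. The size rests on assumptions about onset, duration of detectability and persistence. Section 5.3 attributes poor USS performance partly to fat limiting penetration, a patient trait likely to recur at each round, which points away from independent misses. Joint misses do not always vanish: under section 11.2, interval cancers and HCCs found through AFP-triggered contrast MRI count as false negatives for both tests. The stage objective is descriptive, and no stage-shift test is planned.

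**Conclusion.** The point holds as one about what the primary outcome estimates. As scored, it is paired sensitivity at the round in which HCC is first diagnosed, all rounds combined. It does not estimate 30 months of surveillance with either test alone. If nceMRI is more sensitive, as section 11.3 assumes, and misses are neither fully persistent nor much more persistent for USS than for nceMRI, the measured gap exceeds the stand-alone gap. At 80% and 50% the excess runs from about 21 points (independent misses) through about 4 (latent correlation 0.95) to nil. The documents do not show where in that range the truth lies.

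A reader might infer that the trial is certain to overstate the advantage of nceMRI by some 20 points, that the test is invalid, or that surveillance should have continued after diagnosis. The documents support none of these. The first takes the extreme of an assumed range as fact, and the other two mistake a labelling fault for a design fault. The calculation covers HCC confirmed in the round of detection. LI-RADS 3 or 4 lesions under interval imaging also suspend both tests and were not modelled.

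**What to change.** 1. In sections 3, 6 and 11.2, rename the outcome *paired sensitivity at the round in which HCC is first diagnosed, all rounds combined*, and state that it does not estimate 30 months of single-modality surveillance.
2. Add a bounding analysis for each test's stand-alone 30-month sensitivity. The lower bound is the test as scored. The upper bound also counts as detectable every HCC scored false negative for that test but diagnosed before visit 6 through the other test or through an AFP-triggered contrast-enhanced MRI. Without the AFP-triggered cases it would not be an upper bound.
3. Show stage at diagnosis by detection pattern (both, nceMRI only, USS only, neither) instead of as two overlapping counts.

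This costs wording in three sections and a little analysis on data already collected, with no extra scans or participants. The price is a narrower headline claim and bounds that may be wide.

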7. STUDY DESIGN

This will be a single-arm, multi-centre, prospective cohort study evaluating the diagnostic accuracy of nceMRI and USS for diagnosis of HCC in people at high risk of HCC. People at high risk of HCC include those with liver cirrhosis and a high risk of HCC, or those with previous successfully treated HCC who are back in surveillance with USS. Participants will be recruited from UK hospital-based liver clinics over a period of 18 months and study procedures will take place in UK hospitals and academic centres. Participants will undergo 6 rounds of 6 monthly surveillance with nceMRI and USS over 30 months. Participants will be invited to complete questionnaires at each study visit. Relevant data will also be extracted from the participants' medical records. If at any surveillance round, a surveillance test raises a concern for the presence of HCC, participants will undergo full diagnostic contrast enhanced MRI (ceMRI) to determine whether HCC is present or not. In cases where indeterminate lesions for HCC are reported, these may require further tests including contrast CT, follow-up contrast enhanced MRI, or biopsy as directed by the clinical team. All participants will undergo diagnostic full contrast enhanced MRI at the end of their study participation. If an HCC is diagnosed at any point in the study, then participants will receive treatment according to standard clinical protocols as part of standard of care.

Long-term follow up of medical records from NHS England, the NHS Central Register for Scotland and other patient registries may be conducted for up to 10 years after the end of the active follow up phase. Data obtained from these registries will include but is not limited to liver disease, decompensation episodes, HCC diagnosis, liver transplantation and death. There will be no additional involvement from study sites or participants, as the long-term follow up only involves accessing centrally held medical data.

The overall study design and participant flow is summarised in Figure 1.

Figure 1: AMULET study design and patient flow

Abbreviations: HCC: hepatocellular cancer; USS: ultrasound scan; nceMRI: non-contrast enhanced MRI; AFP: alpha-fetoprotein; HADS: hospital anxiety and depression scale; +ve: positive; -ve: negative [#] see section 9.4 for the description of the procedure for HCC risk estimation

^A contrast enhanced MRI scan may be needed depending on AFP levels (see section 11.2) *Indeterminate lesions will be those that are not definitely HCC and not definitely benign (LI-RADS 3 or LI-RADS 4). The local HCC multidisciplinary team will determine how these are followed up (assessment with alternative imaging modality, interval contrast enhanced scan, biopsy or another follow-up strategy). For the analysis of sensitivity and specificity that will be conducted over the 30 months of follow-up, cases where surveillance tests identified indeterminate lesions, will be counted as true

positives if the lesion progresses to HCC by the end of follow-up and as false positive if they remain indeterminate or are subsequently classed as definitely benign. For the analysis that will be conducted for each surveillance round, the number of indeterminate lesions identified by nceMRI and / or USS will be recorded.

